study, the Sponsor expects systemic exposure of UBX1325 following IVT treatment to be low in patients and, therefore, the potential to observe such systemic events is also low.
Tier	Objective	Endpoints
Primary	Assess the local and systemic safety and tolerability following a single-dose IVT injection of UBX1325 in patients with DME	• Ocular and systemic safety and tolerability of a single IVT injection of UBX1325 evaluated by treatment emergent adverse events (TEAEs)
Secondary	Assess the biological activity following a single UBX1325 injection in patients with DME Assess further efficacy parameters and retinal structure improvement of patients following a single UBX1325 injection compared to sham	 Changes in BCVA from Baseline to Weeks 12, 24 and 48 Proportion of patients who require 2 or more anti-VEGF rescue over 12, 24 and 48 Weeks Change in CST from Baseline to each study visit as assessed by SD-OCT and read by a Reading Center Change in CST area under the curve (AUC) from baseline to each study visit Proportion of patients without macular fluid at Weeks 12, 24 and 48 as assessed by SD-OCT
Exploratory	Assess further efficacy parameters and retinal structure improvement of patients followinga single UBX1325 injection compared to sham	 Change from Baseline in Diabetic Retinopathy Severity Scale (DRSS) score at Weeks 24 and 48 Change in capillary perfusion from Baseline to Weeks 12, 24 and 48 as assessed by OCT-A and FA

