The statistical analysis plan (SAP) provides the detailed methodology for summary and statistical analyses of data collected in study UBX1325-02. This SAP is based on the Protocol Version 5.0 Amendment 4 dated 14 February 2022. Specifications for tables, figures, and listings will be provided in a separate document.

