1.3.2 Secondary endpoints

- Change in Best corrected visual acuity (BCVA) from Baseline to Weeks 12, 24, and 48
- Proportion of patients who require 2 or more anti-VEGF rescue over 12, 24, and 48 Weeks
- Change in CST from Baseline to each study visit as assessed by spectral domain optical coherence tomography (SD-OCT) and read by a Reading Center
- Area under the curve (AUC) of change from baseline of CST for each study visit

- Area under the curve (AUC) of change from baseline of BCVA for each study visit
- Proportion of patients without macular fluid at Weeks 12, 24, and 48 as assessed by SD-OCT
- 1.3.3 Exploratory endpoints
 - Change from Baseline in Diabetic Retinopathy Severity Scale (DRSS) score at Weeks 24 and 48
 - Change in capillary perfusion from Baseline to Weeks 12, 24, and 48 as assessed by Optical Coherence Tomography Angiography (OCT-A) and Fluorescein Angiography (FA)

2. Study Methods

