7.1 Secondary endpoints

The following continuous secondary efficacy endpoints will be analyzed using mixed models for repeated measures (MMRM):

- Change in BCVA from Baseline to Weeks 12, 24, and 48
- Change in CST from Baseline to each study visit as assessed by SD-OCT and read by a Reading Center
- Area under the curve (AUC) of change from baseline of CST for each study visit
- Area under the curve (AUC) of change from baseline of BCVA for each study visit

The MMRM will be used for the primary analysis of the change from baseline in BCVA, which is based on the ETDRS VA chart assessed at a starting distance of four meters. The model will include the change from baseline at Day 2, Week 1 to Week 48 as the dependent variable, and the independent variables will include continuous BCVA baseline, categorical treatment arm

(active or sham), categorical study visit, and arm-by-visit interaction. Within-subject correlation will be modeled using subject-specific random intercepts. The model will assume a compound symmetry covariance structure. If there are convergence problems with this model, then other covariance structure may be fitted. The primary analysis will be limited to data collected prior to or on the rescue date. A supportive analysis will be performed for all data collected, regardless of rescue therapy. Subjects who violated major inclusion or exclusion criteria will be excluded from the primary and supportive analyses.

When BCVA outliers occur, a sensitivity analysis excluding the outliers will be performed. If deemed appropriate, other sensitivity analyses may also be considered to assess the impact of outliers.

The change from baseline in CST, as assessed by SD-OCT and read by a Reading Center, AUC of change from baseline in BCVA and CST, will be analyzed using MMRM, same as the analysis of BCVA.

The following binary secondary efficacy endpoints will be summarized:

- Proportion of patients who require 2 or more, or 1 or more anti-VEGF rescue over 12, 24, and 48 Weeks
- Proportion of patients without macular fluid at Weeks 12, 24, and 48 as assessed by SD-OCT

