9.2 File management and data security

Data and program files will be managed according to BSSI SOP-OP-002, Folder and File Structure Management. Electronic file security and integrity will be protected by procedures outlined in BSSI SOP-IT-002, Data Security.

10. Changes in the Statistical Analysis Plan from the Protocol Analysis Plan

The definition of the Full Analysis Set has changed from the protocol to be based on BCVA instead of CST. The area under the curve (AUC) of change from baseline of BCVA for each study visit has been added as a secondary efficacy endpoint.

11. References

AAO PPP DME Guidelines (2019) available at https://www.aaojournal.org/article/S0161-6420(19)32092-5/pdf

Chan, I. S. F., and Zhang, Z. (1999). Test-Based Exact Confidence Intervals for the Difference of Two Binomial Proportions. *Biometrics* 55:1202–1209.

Coney JM. (2019) Addressing unmet needs in diabetic retinopathy. *American Journal of Managed Care* 25:S0.

12. Appendices

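### AUC of BCVA and CST change is undefined and analysed with a constant-variance model; if cumulative, its last-visit standard error comes out at about half the true value

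*SAP*

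**What the plan says.** SAP 1.3.2 and 7.1 list two AUC endpoints among the secondary endpoints, for CST and for BCVA. The BCVA one reads "Area under the curve (AUC) of change from baseline of BCVA for each study visit". SAP section 10 records that it is new relative to the protocol: "The area under the curve (AUC) of change from baseline of BCVA for each study visit has been added as a secondary efficacy endpoint". The protocol's endpoint table (section 3) has only the CST version: "Change in CST area under the curve (AUC) from baseline to each study visit".

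For the analysis, SAP 7.1 says "AUC of change from baseline in BCVA and CST, will be analyzed using MMRM, same as the analysis of BCVA". The BCVA model has baseline, arm, visit and arm-by-visit terms, and "Within-subject correlation will be modeled using subject-specific random intercepts. The model will assume a compound symmetry covariance structure". The only route to another structure is: "If there are convergence problems with this model, then other covariance structure may be fitted". No robust standard error is named. On rescue: "The primary analysis will be limited to data collected prior to or on the rescue date". A supportive analysis uses all data.

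SAP 3.4 and 3.6 plan analyses at Weeks 12 (formal interim), 24 and 48, and SAP 3.1 sets 95% confidence intervals. Neither document gives a formula, integration rule, time scale or missed-visit rule for AUC. SAP section 1 adds: "Specifications for tables, figures, and listings will be provided in a separate document".

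**The concern.** A random-intercept, compound-symmetry model assumes the same variance at every visit. That may be tolerable for change from baseline. It cannot hold for an AUC that accumulates from Day 1, because a one-week AUC and a 48-week AUC are on very different scales. The fitted variance is an average over visits. It is too small at the last visit of the cut, which is the one each planned analysis is named for.

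The fallback does not protect against this: a model with the wrong variances converges without difficulty.

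The missing definition matters separately. In SAP Appendix B the Visit 12 window runs from Day 309 to Day 519. If actual days are used, a Week 48 AUC could span (309 − 1)/7 = 44 to (519 − 1)/7 = 74 weeks.

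The trial asks whether a single injection has durable activity, and AUC is its summary of benefit over time. With about 62 patients, intervals at half their proper width could make a null AUC difference look like durable activity.

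**Working it through.** **The plan's own figure.** The only stated calculation is the sample size for BCVA change (SAP 2.4): difference 8 letters, SD 13, two-sided 0.15, 80% power, 5% drop-out. A two-sample t-test needs 29 per arm (power 81.1%). Then 29/0.95 = 30.5, rounded up to 31 per arm, or 62. This reproduces. No figure is given for AUC.

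**Inputs.**
- Visits, from the schedule: Days 2, 8, 15, 29, 57, 85, 127, 169, 225, 281 and 337 for BCVA; the same without Day 2 for CST.
- Data cuts at Weeks 12, 24 and 48 (Days 85, 169 and 337).
- SD 13, from SAP 2.4. A constant SD and the sample size both cancel in the ratio below.
- Correlation between visits: not in the documents, so assumed. Fifteen patterns (exchangeable 0.2–0.95; serial decay 0.3–0.95 per 28 days; four mixtures) were crossed with seven SD paths (13 throughout; or 4, 6 or 8 rising to 13 by Week 12 or Week 48), giving 105.

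**Formula.** AUC is the trapezoid sum from Day 1 (change = 0) to visit *t*. With complete data and arm-by-visit terms, the fitted variance at every visit is the mean of the true visit variances in the cut. Hence

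model SE / true SE at visit *t* = √[ mean over visits of Var(AUC) ÷ Var(AUC at *t*) ].

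**Worked example: BCVA, SD 13, exchangeable correlation 0.6, letter-weeks.**
- True SD of AUC at Day 2 and Weeks 1, 2, 4, 8 and 12: 0.93, 10.8, 21.7, 43.1, 86.5 and 128.9.
- Week 12 interim: the six variances sum to 26,543; the mean is 4,424 and its root 66.5. Ratio 66.5/128.9 = 0.52.
- Week 48: the eleven variances sum to 670,307; the mean is 60,937 and its root 246.9. Ratio 246.9/502.0 = 0.49.
- With 31 per arm, the Week 12 SE should be 128.9 × √(2/31) = 32.7; the model gives 66.5 × √(2/31) = 16.9.

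**Cumulative AUC, complete data, all 105 patterns (model SE / true SE at the last visit of the cut).**

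| | Week 12 | Week 24 | Week 48 |
|---|---|---|---|
| BCVA | 0.48–0.55 | 0.46–0.55 | 0.44–0.55 |
| CST | 0.52–0.59 | 0.49–0.58 | 0.46–0.58 |

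Coverage of a 95% interval is 2Φ(1.96 × ratio) − 1: 61% at 0.44, 69% at 0.52 and 75% at 0.59. At the sizing level of 0.15, type I error is 2[1 − Φ(1.44 × ratio)]: 0.53, 0.45 and 0.40.

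**Drop-out and rescue (BCVA only).** Simulated with 31 per arm, no effect, no baseline covariate, five covariances and 400 trials per scenario. Rescue was triggered by the BCVA criterion alone, at assumed rates, because the documents give none.

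| Last-visit ratio | Week 12 | Week 24 | Week 48 |
|---|---|---|---|
| 5% drop-out | 0.49–0.53 | 0.46–0.54 | 0.42–0.52 |
| 30% random loss | 0.48–0.51 | 0.44–0.51 | 0.39–0.47 |
| Rescue cut, 34–88% left pre-rescue at Week 48 | 0.47–0.51 | 0.42–0.49 | 0.35–0.46 |

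A heavier rescue pattern leaving about 11% was also run and is outside the last row. Including it, type I error as written at nominal 0.15 reached 0.57, 0.66 and 0.75 at the three visits.

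**Earlier visits in later cuts.** The Week 12 AUC read from the 48-week model has a ratio of 1.38–2.91 (BCVA) or 1.47–3.12 (CST) on complete data. In the example it is 246.9/128.9 = 1.92. With rescue cuts it is 0.81–2.30 (BCVA), so the direction is not fixed.

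**Other readings of AUC.**
- Time-averaged: 0.86–1.16 at the Week 12 interim if SD is constant. At Week 48, 0.92–1.18 under constant or slowly decaying correlation and up to 1.59 under fast decay. As low as 0.67 at either visit if SD rises steeply (4 to 13).
- Area between consecutive visits: 0.51–0.70 at the last visit.

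**The case against.** The strongest reply is that the half-size SE depends on one reading. The SAP's own phrase does not say cumulative, the protocol wording that suggests it covers only CST, and the separate table specification may settle the matter. That stands as a condition: what is certain is that the two documents leave AUC undefined. But no reading is safe by default. The time-averaged version can still give 0.67 to 1.59, and the interval version 0.51 to 0.70.

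Second, the SAP sets no hypothesis, alpha level or decision rule for AUC, so type I error describes a test the plan does not specify. This is fair. Interval coverage is the figure tied to the SAP's text, and the type I values only illustrate.

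Third, the rescue simulations use invented rates, ignore the CST trigger and omit the baseline covariate. Also fair: they show only that loss and rescue did not shrink the last-visit error in the cases tried. The main result rests on the complete-data calculation, which also bears on the supportive all-data analysis.

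Fourth, a 74-week AUC would need a visit about 26 weeks late, against a scheduled window of ±7 days. It is a bound that the rules permit, not an expectation.

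Finally, impact is limited: safety is primary, and BCVA and CST change are reported directly.

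**Conclusion.** The concern holds. The SAP fixes the model for AUC but not the definition on which the model's validity depends. Under the cumulative reading, the AUC difference at the last visit of each planned analysis carries 0.44 to 0.59 of its true SE on complete data, and 95% intervals cover about 61% to 75%. This assumes trapezoid integration on scheduled days and model-based SEs. It depends little on the unknown correlation. If AUC is divided by elapsed time, most of the Week 12 interim error goes when the SD of change is constant, though not in every pattern tried. AUC is secondary and drives no stated decision, so this should be fixed but does not threaten the trial's primary objective. Confidence is medium because the definition and the covariance are unknown.

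**What to change.** 1. **Define AUC in the SAP.** State the trapezoid rule from Day 1 (change = 0) through each scheduled visit, planned or actual days, how a missed visit is bridged, and whether the result is cumulative (letter-weeks, µm-weeks) or divided by elapsed time. If the table specification already says this, copy it in.

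2. **Do not fit AUC with the constant-variance model.** Suggested text: *The AUC difference at each visit is the trapezoid-weighted contrast of the visit LS-mean differences from the BCVA (or CST) repeated-measures model, with robust (sandwich) standard errors.* A heterogeneous-variance covariance for that contrast is an acceptable alternative. Fitting a heterogeneous-variance model to AUC itself also works, but less well under frequent rescue (type I error up to 0.27 at Week 48, nominal 0.15). The covariance of the BCVA and CST change models need not change for this purpose.

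**Cost.** SAP wording and a little programming; no new data. Last-visit AUC intervals become about twice as wide under the cumulative reading. The corrected method is approximate at this sample size. With no effect, the robust contrast gave type I error of 0.12–0.19 at nominal 0.15 and 93–96% coverage. A second simulation, including an 8-letter effect with unequal rescue, gave 0.11–0.21 and 90–98%, against 36–78% coverage as written. Some bias remains at Week 48 when rescue is frequent and correlation decays. If rescue is very frequent, an arm may have too few pre-rescue patients for a Week 48 AUC by any method (up to 107 of 400 simulated trials with about 11% left).

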8.5 Efficacy Analysis

The Full Analysis Set will be used for all efficacy analyses.

The BCVA will be assessed using the ETDRS chart starting at 4 meters at each study visit. Change in BCVA from baseline to each visit will be analyzed by mixed model for repeated measures (MMRM). The details of MMRM and the analysis methods for other efficacy endpoints described in Section 3 will be provided in the SAP.

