3.7 Multiple testing and error control

No formal adjustment for multiple comparisons is planned.

4. Analysis Populations

Full Analysis Set

The Full Analysis Set will include all randomized subjects who received a single IVT treatment of UBX1325 or sham, have a baseline BCVA assessment, and at least one post-baseline BCVA assessment. The Full Analysis Set will be the primary population for evaluating all efficacy variables. For analysis, subjects will be grouped by randomized treatment arm.

Safety Analysis Set

The Safety Analysis Set includes all patients who received a single IVT treatment of UBX1325 or sham. The Safety Analysis Set will be the primary population for evaluating all safety variables and subject characteristics. For analysis, subjects will be grouped by actual treatment received.

5. Subject Disposition

The number of patients screened, screen failed and the reasons that patients did not qualify for this study will be summarized for the study as a whole. The following data will be summarized for each treatment arm and overall, for all screened subjects:

- Randomized
- Treatment administered
- Completed study
- Did not complete study and reason
- Patients in each analysis population (Full, Safety) randomized

A protocol deviation listing will be provided that includes the start/end date of the deviation and the deviation description. A listing of subject disposition data will also be provided.

6. Demographics and Baseline Characteristics

Demographics and baseline characteristics, including medical history, prior and concomitant medications, will be summarized using the Safety Analysis Set. These data will be listed and summarized for the study overall, as well as for each treatment arm.

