7.2 Exploratory endpoints

Exploratory endpoints include

- Change from Baseline in Diabetic Retinopathy Severity Scale (DRSS) score at Weeks 24 and 48
- Change in capillary perfusion from Baseline to Weeks 12, 24, and 48 as assessed by Optical Coherence Tomography Angiography (OCT-A) and Fluorescein Angiography (FA)

Change from Baseline in DRSS score will be presented as the proportion of patients with a \geq 2step improvement in diabetic retinopathy (DR) severity from baseline on the ETDRS DRSS at Weeks 24 and 48. The proportion of patients with a \geq 2-step improvement in diabetic retinopathy (DR) severity from baseline will be analyzed using the analysis method following those for the binary secondary efficacy endpoints.

For change in capillary perfusion from Baseline to Weeks 12, 24, and 48, the analysis method will follow those for the continuous secondary efficacy endpoints.

Key parameters of OCT-A and FA will be summarized, and all OCT-A, FA and CFP data will be listed.

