7.3 Subgroup Analyses

The following subgroups will be analyzed with respect to two secondary efficacy endpoints: change in BCVA from Baseline to Weeks 12, 24, and 48, and change in CST from Baseline to each study visit.

- Baseline BCVA (≤60 letters and >60 letters)
- Baseline CST (\leq 400 µm and >400 µm)
- Baseline DR severity (<47, ≥47 DRSS score)
- Baseline HbA1c (≤7% and >7%)

The analysis method will be the same as specified above for each respective endpoint. The subgroup categories may be adjusted if there is not enough representation of a specific subpopulation or treatment group. Additional analysis of BCVA and CST with the subgroup as covariate may be performed if clinically significant subgroup difference is observed in the subgroup analysis.

8. Safety Analysis

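### SAP 7.1 drops violators of undefined major eligibility criteria from both the primary and the supportive BCVA, CST and AUC models, so no planned model uses the full FAS if any violators exist

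*SAP*

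**What the plan says.** Protocol 8.5: "The Full Analysis Set will be used for all efficacy analyses". SAP section 4 agrees: "The Full Analysis Set will be the primary population for evaluating all efficacy variables". As the SAP defines it, the FAS requires randomisation, treatment, a baseline BCVA and at least one later BCVA. It sets no eligibility condition.

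SAP 7.1 then describes two BCVA models. The primary MMRM uses data up to the rescue date. The second is wider: "A supportive analysis will be performed for all data collected, regardless of rescue therapy". The paragraph ends with: "Subjects who violated major inclusion or exclusion criteria will be excluded from the primary and supportive analyses".

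CST change and the AUCs of BCVA and CST change "will be analyzed using MMRM, same as the analysis of BCVA", so the exclusion reaches them by reference. For capillary perfusion, SAP 7.2 says "the analysis method will follow those for the continuous secondary efficacy endpoints". For subgroups, SAP 7.3 says "The analysis method will be the same as specified above for each respective endpoint". Whether the exclusion carries over to those two sets of analyses is an inference from the word *method*. No exclusion is stated for the rescue, macular-fluid or DRSS endpoints.

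SAP section 10 declares two changes from the protocol. One is "The definition of the Full Analysis Set has changed from the protocol to be based on BCVA instead of CST". The other is the added BCVA AUC endpoint. The exclusion of eligibility violators is not declared.

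**The concern.** There are three problems.

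- **The populations conflict.** The protocol and SAP section 4 name the FAS, while SAP 7.1 models a subset of it. The departure from the protocol is not declared.
- **The effect of the exclusion cannot be seen.** The supportive model relaxes only the rescue cut-off and carries the same exclusion. The one firm sensitivity analysis removes BCVA outliers, so it takes out more data and restores none.
- **The rule is not fixed.** Neither document ranks the criteria in protocol 4.5 and 4.6, and some of them rest on investigator opinion. Nothing says who classifies violations, whether they are masked, or that the list is settled before the formal Week 12 analysis. Protocol 6.6 masks the Sponsor, but SAP 2.3 allows for some unmasked Sponsor roles.

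BCVA change is the endpoint that sizes the trial. An exclusion made under masking on objective pre-randomisation facts need not bias the comparison, but the SAP does not require either condition. With about 29 evaluable patients per arm, each removal has some weight.

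**Working it through.** **Where the populations stand**

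| Analysis | Rescue cut-off | Eligibility violators |
|---|---|---|
| FAS (protocol 8.5, SAP 4) | none | kept |
| Primary MMRM (SAP 7.1) | applied | removed |
| Supportive MMRM (SAP 7.1) | lifted | removed |
| Outlier sensitivity (SAP 7.1) | not stated | not restored |

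No row below the first keeps the violators. Descriptive summaries (SAP 3.1) and listings (SAP 7.1) may include them, but neither gives a model-based comparison.

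**The ambiguity in practice.** SAP 2.2 describes BCVA of 70 to 20 letters and at least one of three agents. Protocol 4.5 has 73 to 20 letters and at least two injections. A patient with 71 to 73 letters meets one text and not the other. The two passages must be reconciled before anyone can say who is a violator.

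**Inputs** (protocol 8.2, SAP 2.4): 31 per arm, 5% dropout, difference 8 letters, SD 13, two-sided 0.15, 80% power.

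**The plan's own figure.** With the noncentral t distribution, 28 per arm gives 79.99% power and 29 gives 81.1%. So 29 are needed, and 29/0.95 = 30.5, rounded up to 31 per arm, or 62 in total. The sample size reproduces.

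**Baseline for the illustration** (one visit, two-sample approximation):

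- Evaluable per arm: n = 31 × 0.95 = 29.45.
- SE = 13 × √(2/29.45) = 3.39; df = 2 × 29.45 − 2 = 56.9.
- Threshold at two-sided 0.15: 1.459 × 3.388 = 4.94 letters.
- Threshold at two-sided 0.05: 2.003 × 3.388 = 6.78 letters.

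**Shift from the exclusion.** The number of violators is not given, so k and d are assumed. Removing k patients from one arm, each d letters from its mean in the same direction, moves the difference by k × d/(29.45 − k). If exclusion is unrelated to outcome, the expected shift is 0, with SD 13 × √(1/(29.45 − k) − 1/29.45).

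| k | Shift, d = 5 | Shift, d = 15 | SD if unrelated | 0.15 threshold after removal |
|---|---|---|---|---|
| 1 | 0.18 | 0.53 | 0.45 | 4.99 |
| 2 | 0.36 | 1.09 | 0.65 | 5.04 |
| 3 | 0.57 | 1.70 | 0.81 | 5.09 |

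**Which results could cross 0.15.** The band is the threshold after removal, minus or plus the shift:

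- k = 1, d = 5: 4.81 to 5.16 letters.
- k = 1, d = 15: 4.46 to 5.52 letters.
- k = 3, d = 5: 4.52 to 5.65 letters.
- k = 3, d = 15: 3.38 to 6.79 letters.

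**At an observed 8 letters**

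| Case | Difference | p | 95% CI |
|---|---|---|---|
| No exclusion | 8.00 | 0.022 | 1.2 to 14.8 |
| k = 3, d = 15, favourable | 9.70 | 0.007 | 2.7 to 16.7 |
| k = 2, d = 15, unfavourable | 6.91 | 0.0502 | just includes 0 |
| k = 3, d = 15, unfavourable | 6.30 | 0.076 | −0.7 to 13.3 |

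**Power** at 8 letters and two-sided 0.15: 81.6% with 29.45 per arm, 80.5% with 28.45 and 79.3% with 27.45.

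**The case against.** The strongest reply is that the point is conditional and small. With no violators the modelled set is the FAS, and the protocol works to keep violators out: a central reading center determines CST and DRSS, and eligibility is rechecked at Visit 1 before randomisation. Exclusion unrelated to outcome gives no expected shift. The widest band needs three extreme patients in one arm, all in the same direction. The 0.15 level is used for sizing and is not stated as a decision rule. BCVA is a secondary endpoint in a Phase 2a trial whose primary endpoint is safety. The calculation also ignores data lost after rescue and holds the SD fixed, so it is an illustration and not a bound. All of this stands, and it limits the severity.

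Other replies carry less weight. Protocol 8.5 leaves the details of the MMRM to the SAP, but the same section fixes the population. Protocol 8.6.1 permits further exploratory analyses, so an FAS model could be run, but none is planned. SAP 3.6 bases the Week 12 analysis on every randomised patient. That describes whose data enter the interim, and it specifies no separate MMRM population. The statement that no unmasking is planned does not say who classifies violations. The SAP must be final before database lock (protocol 8.1), but that does not fix the list of excluded patients.

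By-arm counts and reasons for exclusion may appear in the separate table specifications, which are not available here. SAP 3.1 does require the analysis N on tables. The SAP itself states no by-arm count of these exclusions, and the deviation listing in SAP section 5 mentions no major or minor class.

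**Conclusion.** The concern holds and should be fixed. As written, SAP 7.1 conflicts with protocol 8.5 and SAP section 4, rests on an undefined term and is not declared in SAP section 10. If any violator exists, BCVA, CST and both AUC endpoints have no planned MMRM on the full FAS. This reading is firm for those endpoints and an inference for capillary perfusion and the subgroups.

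The size is modest. Under the assumed 1 to 3 removals from one arm at 5 to 15 letters, the shift is 0.2 to 1.7 letters, which is 2% to 21% of the planned 8. At an observed 8 letters, p stays below 0.15 in every case examined. The 95% interval that SAP 3.1 plans to report would include zero only in the more extreme unfavourable cases. The main problem is an open choice of who is analysed, with no planned analysis to show what that choice did.

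**What to change.** Run the primary and supportive MMRMs for BCVA, CST and both AUCs, and any analysis that copies them, on the FAS by randomised arm. Move the exclusion of eligibility violators to one labelled sensitivity analysis, with these conditions:

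- List the *major* criteria by their numbers in protocol 4.5 and 4.6, after reconciling SAP 2.2 with protocol 4.5.
- Have patients classified by people masked to treatment arm.
- Date the list before the Week 12 analysis.
- Report exclusions by arm and reason.

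If the exclusion stays in the primary analysis, define it in the same way, declare it in SAP section 10, and add an FAS run for each affected endpoint.

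The preferred route costs SAP wording, one sensitivity table, one by-arm row and a few more model runs. The alternative needs more runs: four endpoints, primary and supportive, could mean eight models. Neither needs new data. The drawback of the preferred route is that a few ineligible patients may add a little noise to the main estimate.
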